Adverse events due to concurrent illnesses other than asthma may be grounds for withdrawal if the illness is considered significant by the study investigator or if the patient is no longer able to effectively participate in the study. Subjects experiencing minor intercurrent illnesses may continue in the study provided that the nature, severity, and duration of the illness are recorded and that any unscheduled medications required to treat the illness are also recorded. Examples of minor intercurrent illnesses include acute rhinitis, sinusitis, upper respiratory infections, urinary tract infections, and gastroenteritis. Medications are allowed for treatment of these conditions in accordance with the judgment of the responsible study physician.

Documentation of an adverse event unrelated to asthma will be recorded on an Adverse Event Report Form and will include the following information:

1. Description of the illness
2. Dates of illness
3. Treatment of illness and dates (medications, doses, and dose frequency)
4. Whether emergency treatment or hospitalization was required
5. Treatment outcome

C. Adverse Events Related to Asthma Exacerbations

Definition - for this protocol, an asthma exacerbation is defined as the development of an increase in symptoms of cough, chest tightness, and wheezing in association with one or more of the following:

- An increase in "as needed" or rescue albuterol use of ≥ 8 inhalations over a 24-hour period above baseline use (baseline defined as average daily use during the period from Visit 1 to randomization at Visit 2), or ≥ 16 total inhalations over a 24-hour period.

- A fall in PEF of $\leq 65\%$ from personal best (personal best is defined as the best of 3 acceptable post-bronchodilator blows on the peak flow meter performed at Visits 1 and 2) or $FEV_1 \leq 80\%$ of baseline

Patients developing asthma exacerbations during the double-blind treatment period and during the off-treatment period will be managed according to the following rescue algorithms. Patients developing asthma exacerbations during the assessment/characterization period will be removed from the study. Once the exacerbation has been resolved the patient may be considered for re-enrollment, starting again with Visit 1.

1. Rescue Algorithms

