A multivariate analysis will be applied in the second stage, such as a bivariate multiple regression analysis for the continuous outcome (the change from baseline with respect to pre-bronchodilator FEV₁) and bivariate logistic regression for the categorical version of the response that uses generalized estimating equations (75). PROC MIXED and PROC GENMOD of SAS 8.2 will be used for these statistical analyses.

Changes to the protocol's eligibility criteria as approved by the Data Safety Monitoring Board and the five clinical sites are anticipated on August 1, 2002. These include 1) allowing either the demonstration of reversibility or a methacholine PC₂₀ ≤ 12.5 mg/ml to qualify subjects, 2) increasing the maximum allowed albuterol use during the assessment/characterization period from once per day on average to four times per day on average, excluding pre-exercise albuterol

use, 3) no longer excluding patients who have a borderline increase in liver enzymes, and 4) no longer excluding patients with morbid obesity. Subjects will be classified according to whether they are eligible under the original entry criteria or the revised entry criteria. Then, the statistical analysis will include a blocking factor to account for this classification.

E. Drop-out Status

Drop-out status is assigned to any randomized child (1) who requires systemic corticosteroids for an asthma exacerbation, (2) who requires another corticosteroid (other than the study ICS or maintenance intranasal corticosteroid) for any illness, (3) who becomes pregnant, (4) who withdraws assent, or (5) whose parent withdraws consent.

If a child is assigned drop-out status, then only that child's data prior to drop-out status will be included in the primary statistical analyses. If a child reaches drop-out status, then the primary outcome variable for any ensuing active treatment period cannot be assessed properly, so these data are excluded. Although this statistical approach is not congruent with an intent-to-treat philosophy, it is warranted because this is an efficacy trial and not an effectiveness trial. The specific aims of the CLIC trial are to characterize children's responses to the active ICS and the LTRA treatments.

F. Missing Data

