Because of the possibility of drop-outs and other missed visits, there will be some missing data. The missing data complicate the planned statistical analyses for the specific aims, described above. With respect to the first specific aim, all available data will be included in calculating the correlation coefficients. For data that are missing, values can be imputed to generate the most extreme cases and the correlation coefficients can be determined under these circumstances. This approach will yield lower and upper boundaries for the estimated correlation coefficients and their confidence limits. In addition, a multiple imputation procedure will be implemented in order to account for the variability that occurs when replacing missing data with imputed values.

With respect to the second specific aim, the statistical analyses in the presence of drop-outs and missed visits is more complex, especially for the bivariate logistic regression analysis with generalized estimating equations (GEE). GEE requires that any missing data satisfy the assumption of "missing completely at random" (MCAR), i.e., the probability of response is independent of the observed and unobserved data (76). The MCAR assumption will be investigated and if it appears that it is violated, then likelihood-based regression models will be

implemented that assume either that the data are “missing at random” (MAR) or are non-ignorable (76).

G. Interim Analyses

The CLIC trial is not a typical effectiveness trial comparing treatments, so formal statistical analyses to evaluate effectiveness at interim time points will not be scheduled. However, an interim statistical analysis to evaluate the safety of the ICS and the LTRA will be scheduled at the midpoint of the trial and the results presented to the Data and Safety Monitoring Board (DSMB). The DSMB also will receive any reports of serious adverse events as they occur throughout the course of the trial.

H. Sample Size Justification

The target sample size for this trial is $N = 140$, and the justification is as follows. With respect to **Research Aim 1**, to test the null hypothesis that the Kendall correlation coefficient is zero versus a specified alternative at significance level α and statistical power $1 - \beta$, the approximate sample size formula is

$$N = 4(z_{1-\alpha/2} + z_{1-\beta})^2 / 9\tau^2$$

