where $z_{1-\alpha/2}$ and $z_{1-\beta}$ represent appropriate percentiles from the standard normal distribution (77). For a two-sided, 5% significance level test with 90% statistical power ($\alpha = 0.05$ and $\beta = 0.10$) against the alternative that $\tau = 0.2$, the required sample size is $N = 117$. However, to account for a maximum of 15% drop-outs and/or missed visits, it is necessary to increase the sample size to $N = 140$.

With respect to the exploratory statistical analyses planned for **Research Aims 2 and 3**, the sample size of 140 is in effect. The target sample size of $N = 140$ is chosen because it provides a 95% confidence interval with endpoints ± 0.15 for a Pearson-type correlation when the true correlation is 0.5 or greater and there is a maximum of a 15% drop-out rate. Although logistic regression analyses will be applied in addition to linear regression analyses (which yield Pearson-type correlations), the estimated parameter coefficients from a maximum likelihood algorithm in a logistic regression model will behave in a similar manner.

A sample size of $N = 210$ would provide a tighter 95% confidence interval than with $N = 140$, with endpoints ± 0.10 for a Pearson-type correlation when the true correlation is 0.5 or greater. Therefore, it may be desirable to recruit this larger number of subjects, if possible.

Recruitment will be monitored to determine whether it is feasible to pursue this larger sample size.

XII. Significance

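### For the exploratory categorical analysis, GEE stays the default unless MCAR appears violated, although the protocol's own drop-out rule makes MCAR implausible

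*Protocol*

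**What the plan says.** Protocol XI.D calls Aims 2 and 3 exploratory and gives them two second-stage models. The continuous FEV₁ change gets a bivariate multiple regression. The categorical version gets a bivariate logistic regression with GEE. PROC MIXED and PROC GENMOD are the procedures named.

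XI.F, writing of the second aim, states that GEE requires MCAR and then sets the rule: "The MCAR assumption will be investigated and if it appears that it is violated, then likelihood-based regression models will be" implemented, under either a missing-at-random (MAR) or a non-ignorable assumption. It gives no criterion for the switch.

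XI.E lists five events that make a randomised child a drop-out. The first is a child "who requires systemic corticosteroids for an asthma exacerbation". Only data from before drop-out enter the primary analyses, and the outcome of any later treatment period is treated as not assessable.

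IV.C, VII.A and VII.E class the same event as treatment failure. Under VII.C, FEV₁ at or below 80% of baseline is one of the alternative signs that, together with increased symptoms, define an exacerbation.

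**The concern.** The plan makes a method that needs MCAR the default and puts the burden on the data to show that MCAR fails. The protocol's own rules already give a reason to doubt it: a child whose asthma worsens enough to need systemic corticosteroids leaves the analysis, and the response in that period goes missing. An event named treatment failure is therefore coded as no information rather than as a poor outcome.

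If the investigation of MCAR shows nothing, the GEE analysis stands. The proportion of poor responders would then tend to be too low, and associations between phenotype or genotype and response would be estimated in a sample from which some of the clearest failures have been removed. Those subgroup findings are what Aims 2 and 3 are meant to supply.

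**Working it through.** **1. The plan's own numbers (XI.H).** Inputs: two-sided 5% level, 90% power, τ = 0.2.

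N = 4(1.960 + 1.282)² / (9 × 0.2²) = 4 × 10.507 / 0.36 = 116.75, so 117, as stated. Allowing for 15% loss, 117 / 0.85 = 137.6, so 138; the plan rounds up to 140. At that maximum loss, 140 × 0.85 = 119 children are complete and 21 are not.

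**2. Drop-out rule against outcome.**
- Outcome (XI.D): change in pre-bronchodilator FEV₁ from Visit 2 to week 8 of each period.
- Exacerbation (VII.C): increased symptoms plus one of several signs, one of which is a fall in FEV₁.
- Consequence (VII.D, XI.E): a child given systemic corticosteroids leaves the study, and later responses are not used.

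MCAR requires the chance of being observed to be unrelated to the response. A rule that removes children for worsening asthma, defined partly through FEV₁, makes that implausible. The other four triggers (another corticosteroid for any illness, pregnancy, withdrawn assent, withdrawn consent) need not depend on response.

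**3. How much a check could show.** The plan names no test. Assume a two-group comparison of a standardised variable at the two-sided 5% level.

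Standard error = √(1/21 + 1/119) = 0.237. Difference detectable with 80% power = (1.960 + 0.842) × 0.237 = 0.66 SD. Power at 0.5 SD is 56%.

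A child lost in period 1 has no week-8 response, and XI.D keeps the first four weeks of each period out of the main analyses, so the check on such a child rests largely on baseline data. If only 10 of the 21 have an observed period-1 response (an assumption), a comparison of that response has 80% power only at (1.960 + 0.842) × √(1/10 + 1/119) = 0.92 SD, and 33% power at 0.5 SD.

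None of this reaches the main difficulty. Dependence on the week-8 value that was never measured cannot be seen in observed data at any sample size.

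**4. Possible size of the bias (illustration by simulation).** From the protocol: montelukast mean 8.23% and SD 13.52% (VI.G, the eight-week paediatric study), a 10% cut for good response (XI.D), and 15% total loss (XI.H). Assumed: inhaled corticosteroid (ICS) mean 10%, the same SD, correlation 0.31 (the normal-theory equivalent of τ = 0.2), and log-odds of drop-out that rise by the given slope for each SD of lower response in the current period.

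| Slope | ICS, full → observed | Montelukast, full → observed | Excess (points) |
|---|---|---|---|
| 0 | 50.0% → 50.0% | 44.9% → 44.9% | 0 |
| 0.5 | 49.8% → 51.5% | 44.7% → 46.4% | 1.7 and 1.7 |
| 1 | 50.0% → 53.0% | 44.8% → 47.8% | 3.0 and 3.0 |
| 2 | 50.0% → 54.3% | 44.8% → 49.3% | 4.3 and 4.5 |

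The level shifts for both drugs. With equal slopes the difference between them hardly moves: at slope 2, 50.0 − 44.8 = 5.2 points in full and 54.3 − 49.3 = 5.0 observed.

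**The case against.** The best case for the plan has four parts.

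- **Scope.** GEE is tied only to the categorical response, in aims the protocol calls exploratory. A reader might infer that all of Aim 2 rests on MCAR. It does not: the continuous regression, if fitted by likelihood in PROC MIXED, is valid under MAR. This stands and limits the point.
- **No test is specified.** Investigating MCAR could include looking at reasons for drop-out, which would show the dependence directly, and such detail may sit in an analysis plan. This stands in part: the 0.66 SD figure applies only if drop-outs are compared with completers. But if the reasons for drop-out are enough to reject MCAR, the rule in XI.E already supplies that reason, and a conditional default serves no purpose.
- **Fallbacks exist.** MAR and non-ignorable models are both named. True, but they are reached only through the check.
- **Exacerbation is not low FEV₁ response.** VII.C also accepts albuterol use or peak flow, and only one of five triggers is directly driven by response. So a reader should not conclude that MCAR is proved false; implausible is as far as the text goes.

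A reader might also infer that the Aim 1 missing-data plan fails, because with τ = 0.20 and 21 children lost the extreme-case limits can span zero. There are 140 × 139/2 = 9,730 pairs, of which 119 × 118/2 = 7,021 are complete, leaving 2,709 free. The limits are (0.2 × 7,021 ± 2,709)/9,730 = −0.13 and +0.42. The protocol does not support that reading. The range needs all 21 children to lose both responses, whereas XI.E keeps data from before drop-out; with one response missing in each, simulation gives about −0.01 to +0.29 before confidence limits. The bounds are optional ("values can be imputed to generate the most extreme cases and the correlation coefficients can be determined under these circumstances"), multiple imputation is firmly planned beside them, and no decision rests on them.

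**Conclusion.** The point holds for the categorical logistic analysis in Aims 2 and 3. MCAR is implausible by the protocol's own drop-out rule, and the plan should not depend on a check to discover this. Such a check would be weak at the maximum planned loss (0.66 SD detectable with 80% power, 21 against 119) and blind to dependence on the unmeasured week-8 value.

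The likely effect is modest: roughly 1.7 to 4.5 percentage points too many good responders at 15% loss, under the assumptions of the illustration. It would be smaller if few losses are exacerbations; the protocol does not give that share or the split of losses between periods. It is tempting to go further and say the analysis will favour whichever drug has more failures. That would need failure-driven loss to differ between the drugs, which the protocol gives no figures to establish, and with equal slopes the contrast in the illustration was almost unchanged.

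The change is worth making because it is cheap and uses tools the plan already names. The primary mixed model, the continuous Aim 2 and 3 regression and the Aim 1 analyses are not called into question here.

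**What to change.** In XI.F, for the categorical response only:

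1. Remove the MCAR pre-test. Make a likelihood-based model valid under MAR, or GEE after multiple imputation, the default.
2. Report, whatever any check shows, an analysis that scores protocol-defined treatment failures as poor in the period of failure. MAR alone does not cover this loss: a child who fails in period 1 has no observed week-8 response from which the missing one could be inferred.
3. Report, also in every case, a non-ignorable sensitivity analysis, for example a stated series of downward shifts applied to imputed responses.

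Scoring failures as poor changes what is estimated, and XI.E gives an efficacy rationale for excluding data after drop-out. The scored analysis therefore belongs beside the default, not in place of it. State whether corticosteroid use for an unrelated illness, which VII.E also counts as treatment failure, is scored the same way. The lists of treatment failure and drop-out events must be reconciled first: IV.D and VII.F give only pregnancy and withdrawal as drop-out, while VII.A, VII.D and XI.E add corticosteroid use.

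The continuous model needs no change of default, and the Aim 1 bounds may stay as a worst-case display beside the multiple imputation. The cost is wording, a fuller model specification than GEE needs, and a little programming. No visits, data collection or sample size change.

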Poor response to leukotriene antagonists could be related to low leukotriene synthesis. To date, several pharmacogenetic associations have been identified for leukotriene synthesis. One is related to decreased leukotriene production (ALOX5 promoter genotype) and another related to increased leukotriene synthesis (LTC-4 synthase). The latter is present in aspirin-sensitive asthmatics (64). A predisposition to increased leukotriene synthesis could be associated with a good response to a leukotriene antagonist. The frequency of ALOX5 promoter genotypes has

been described with associated response to an inhibitor of the 5-lipoxygenase pathway (65, 66). This study demonstrated a poor response to a 5-lipoxygenase inhibitor in a mutant ALOX5 genotype. A similar observation could occur with a leukotriene antagonist where low production of leukotrienes would be associated with an absence of effect with a leukotriene antagonist.

Available reports indicate that both fluticasone propionate (37, 38) and montelukast are metabolized through the cytochrome P4503A4 family. In addition, montelukast is metabolized through the cytochrome P450 2C9 pathway (39, 40). Considerable information is now available regarding the features of this cytochrome family (67-70). Detailed information on the metabolic pathways of both medications will be obtained and considered for evaluation of cytochrome P450 genotype based on considerations of race, age, and functional differences in genetic polymorphisms.

A blood sample for genetic analysis will also be obtained from both parents in order to evaluate transmission of genetic polymorphisms of interest. An initial plan for proceeding with analysis will be provided in the Anticipated Results and Analysis sections.

C. Duration

The duration of the study will be approximately 14 months with an anticipated onset date of January 1, 2002 and an anticipated end date of February 28, 2003. Children will be enrolled over a 9-month period and each child will complete the study over approximately a 5-month period. If recruitment for the 140 subjects is successful, consideration will be given to extending the recruitment four additional months for the recruitment of 210 subjects, with an anticipated study end date of June 30, 2003.

VI. Protocol

A. Recruitment

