If subject accrual becomes problematic related to the need to recruit specific, less common, asthmatic phenotypes, this center will develop strategies to expand the recruitment net to the outlying areas outside of Madison. According to the state vitals office, the entire Dane County area had 5,125 births in 1998, while the total population census was 409,910. Milwaukee

County, about 1 hour from the UW campus, has a population census of approximately one million. The Children's Hospital of Wisconsin is located in Milwaukee and their Allergy/Asthma program has expressed a keen interest in becoming involved in CARE Network-initiated trials.

B. Drug Supplies

Drug supplies for this study will consist of one inhaled corticosteroid (ICS), fluticasone propionate (Diskus®, Glaxo Wellcome, 100 mcg per inhalation) and corresponding placebo; one oral tablet, montelukast tablets (Singulair, Merck, 10 mg oral tablet and 5 mg chewable tablet) and corresponding placebos, and albuterol MDI rescue inhaler. These will be purchased or provided by Glaxo Wellcome and Merck, as needed.

1. For montelukast, drug supply will be needed for 140 subjects (28 subjects per clinical center) to complete the study. Allowing for as many as 42 randomized subjects per clinical center requires drug supplies for 210 subjects. Based on the study design of one active eight-week treatment period with montelukast, a ten-week supply is needed for each randomized subject. Given the age distribution anticipated for this trial, approximately one-third of the subjects will require the 10 mg tablets and two-thirds will require the chewable 5 mg tablets. Thus, approximately 4,900 10 mg tablets are needed and 9,800 chewable 5 mg tablets are needed. For each subject, and one ten-week supply of placebo montelukast tablets are needed for the randomized treatment period that the subject receives active fluticasone. This translates into approximately 4900 placebo 10 mg tablets and 9,800 placebo chewable 5 mg tablets..

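### Section XI.H: at a true correlation of 0.5, 210 randomised children give about ±0.12, not the stated ±0.10

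*Protocol*

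**What the plan says.** Protocol Section XI.H (Sample Size Justification) gives two precision statements for Research Aims 2 and 3, both for a 95% confidence interval on a Pearson-type correlation.

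- For N = 140 the endpoints are ±0.15, "when the true correlation is 0.5 or greater and there is a maximum of a 15% drop-out rate".
- N = 210 "would provide a tighter 95% confidence interval than with" N = 140, with endpoints of ±0.10 under the same condition on the true correlation. This sentence does not mention drop-out.

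The section then concludes: "Therefore, it may be desirable to recruit this larger number of subjects, if possible".

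Elsewhere the 210 is a count taken before any loss. Section V.C (Duration) says "consideration will be given to extending the recruitment four additional months for the recruitment of 210 subjects", and Section VI.B (Drug Supplies) says "Allowing for as many as 42 randomized subjects per clinical center requires drug supplies for 210 subjects". The general allowance in Section XI.H is made "to account for a maximum of 15% drop-outs and/or missed visits".

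**The concern.** The width of a confidence interval for a correlation falls roughly with the square root of the sample size. Multiplying the sample by 1.5 should narrow the interval by a factor of about √1.5 = 1.22. The two stated figures differ by a factor of 0.15/0.10 = 1.5, which is the ratio of the sample sizes themselves. One of the two figures must therefore be off, or they rest on different assumptions although the text compares them directly.

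The extension would mean 70 more children and four more months of recruitment, and the only statistical reason offered for it is this gain in precision. If the gain is overstated, the sponsor weighs that burden against a benefit that 210 children do not provide.

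**Working it through.** **Inputs.** Confidence level 95%, a true correlation of 0.5 or greater, the two sample sizes and the 15% loss all come from Section XI.H. The interval narrows as the correlation rises, so 0.5 is the least favourable value covered by the claim. Sections V.C and VI.B show that 210 is a recruited and randomised number. The protocol names no interval method. I used the Fisher z interval and, as a check, the simple large-sample half-width.

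**Evaluable children with 15% loss.**
- 140 × 0.85 = 119
- 210 × 0.85 = 178.5, taken as 178

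**Formulas.**
- Fisher z: limits = tanh(atanh(r) ± 1.96/√(n − 3)), with atanh(0.5) = 0.5493
- Large-sample half-width: 1.96 × (1 − r²)/√(n − 1), which at r = 0.5 is 1.47/√(n − 1)

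**Step 1: the plan's figure for N = 140.** With n = 119, 1.96/√116 = 0.182. The limits are 0.352 and 0.624, that is -0.148/+0.124. The stated ±0.15 is the longer limb. The mean half-width (0.136) and the large-sample half-width (0.135) would each round to 0.14.

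**Step 2: N = 210 on the same basis.** With n = 178, 1.96/√175 = 0.148. The limits are 0.381 and 0.603, that is -0.119/+0.103. The longer limb is about 0.12. Scaling the plan's own figure agrees: 0.15 × √(140/210) = 0.122.

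**Step 3: all readings at a correlation of 0.5.**

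| Evaluable | Lower limb | Upper limb | Mean half-width | Large-sample half-width |
|---|---|---|---|---|
| 119 (140 randomised, 15% loss) | 0.148 | 0.124 | 0.136 | 0.135 |
| 178 (210 randomised, 15% loss) | 0.119 | 0.103 | 0.111 | 0.110 |
| 210 (no loss) | 0.109 | 0.095 | 0.102 | 0.102 |

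No column gives both 0.15 in the first row and 0.10 in either of the others.

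**Step 4: size needed for ±0.10 at a correlation of 0.5.**
- Longer limb: atanh(0.5) − atanh(0.4) = 0.5493 − 0.4236 = 0.1257, and (1.96/0.1257)² + 3 is just over 246. This means 247 evaluable, or 247/0.85 = 291 randomised.
- Mean half-width: 219 evaluable, 258 randomised.
- Large-sample half-width: (1.47/0.10)² + 1 = 217.1, so 218 evaluable, 257 randomised.

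**Step 5: where ±0.10 does hold.** With 178 evaluable, the longer limb falls to 0.10 only once the true correlation reaches about 0.62 (about 0.57 on the mean half-width). With all 210 evaluable the thresholds are about 0.56 and 0.515.

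**The case against.** The best defence is that the N = 210 sentence states no drop-out. Read literally, with 210 children analysed, the large-sample and mean half-widths are both 0.102, which rounds to 0.10. That is arithmetically right, but it requires two changes from the sentence it is compared with. It drops the 15% loss, although 210 is a randomised count, and it uses a method that gives 0.135 or 0.136 rather than 0.15 at 119 evaluable.

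A second defence is that both figures may be rounded to the nearest 0.05: 0.136 would become 0.15 and 0.111 would become 0.10. The protocol states no such rounding. If that is what was done, rounding turned a gain of 0.136 − 0.111 = 0.025 into 0.05, so the comparison would still mislead.

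Other points do stand and limit the weight of the finding:
- The absolute shortfall is only 0.01 to 0.02.
- Aims 2 and 3 are described as exploratory.
- The extension is optional and depends on feasibility. No rule makes it turn on reaching ±0.10, and nothing shows that ±0.12 would change the decision.
- N = 210 is still tighter than N = 140.
- A symmetric ±0.12 describes only the longer limb, so a correction should give both limbs.

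**Conclusion.** The ±0.10 is wrong on the basis that yields ±0.15 for N = 140. With 15% loss and a true correlation of 0.5, 210 randomised children give limbs of -0.119/+0.103. The longer limb improves from 0.148 to 0.119, a gain of about 0.03 where the text implies 0.05.

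This rests on two readings. One is that the 15% loss applies to the 210, which the recruitment and drug-supply sections support. The other is that ±0.15 is the longer Fisher z limb, which is inferred because it is the only measure examined that reproduces the figure to two decimals. Relaxing the first still leaves a longer limb of 0.109. Relaxing the second leaves 0.110 or 0.111 at 178 evaluable.

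The Aim 1 calculation is unaffected: the Kendall formula gives 116.7, rounded up to 117, and 117/0.85 = 138 is covered by 140. The correction is worth making because the figure is used as the reason for enlarging the trial, but it is not urgent.

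**What to change.** In Section XI.H, replace the N = 210 sentence with one on the same footing as the N = 140 sentence, for example: with 210 randomised children and the same 15% loss (178 evaluable), the 95% confidence interval at a true correlation of 0.5 extends about 0.12 below and 0.10 above, by the Fisher z method. Name the method for N = 140 as well, so that the two figures can be compared (-0.15/+0.12 against -0.12/+0.10). If the sponsor prefers to keep ±0.10, the text should say that it is a rounded average half-width assuming all 210 children are evaluable.

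The decision on extending recruitment under Section V.C should then rest on the restated figure. The cost is one or two sentences and a slightly less favourable number. No additional children, analyses or procedures are proposed.
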